For intubated patients: any patient 1 month to 17 years old admitted to the pediatric intensive care unit (PICU) or cardiothoracic intensive care unit (CTICU) with asthma, reactive airways or chronic lung disease and is scheduled to receive albuterol or levalbuterol.

For non-intubated patients: any patient 1 month to 21 years old admitted to the pediatric intensive care unit (PICU) or cardiothoracic intensive care unit (CTICU) with asthma, reactive airways or chronic lung disease and is scheduled to receive albuterol or levalbuterol.

c. Exclusion Criteria

1. If intubated, patients with a large endotracheal tube leak (greater than 18%)
2. SpO₂ less than 95 % while receiving an FiO₂ of > 40%, signifying intrapulmonary shunting in which case the use of albuterol or L-albuterol could change the degree of intrapulmonary shunt during the testing.

a. Subject Eligibility – Healthy Volunteers

Healthy volunteers less than 60 years of age available to participate on two consecutive days

b. Inclusion Criteria – Healthy volunteers less than 60 years of age

c. Exclusion Criteria – Any contraindication to use of Albuterol such as known allergy to albuterol or levalbuterol.

Protocol for intubated and non-intubated patients receiving albuterol or levalbuterol

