After obtaining a written informed consent from patients/guardians that are scheduled to receive albuterol or levalbuterol, the subjects will be randomized using pre-prepared opaque sealed envelopes to two different groups, group A and B. The measurements will be done over 2 separate days. On Day 1 Group A will receive albuterol first followed by levalbuterol for when the next dose is due. On day 2 the order will be reversed and therefore levalbuterol will be given first followed by albuterol. Group B will be first given levalbuterol followed by albuterol for the next scheduled dose. If the patient is receiving albuterol as their clinically prescribed medication the levalbuterol dose will be chosen to be ½ that milligram amount. If the patient is receiving levalbuterol as their clinically prescribed medication the albuterol dose will be chosen to be 2 times that milligram amount. Typical dosages in the ICU would be albuterol 0.15 mg/kg with a minimum of 2.5 mg and maximum of 5 mg and levalbuterol 0.63 mg and 1.25 mg respectively. However, if a young child is clinically prescribed a dose of Albuterol of 1.25 mg(max dose of levalbuterol) then the dose of Levalbuterol for the study would be 0.63 mg. Albuterol is only FDA approved for marketing to patients greater than 2 years of age but it has been used clinically at all age levels. Likewise, Levalbuterol has been used clinically in infants and children but is only FDA approved for marketing to patients greater than 6 years of age. Measurements of oxygen consumption will be done using the non-invasive device Innocor. This device has been validated for measurement of oxygen consumption against the gold standard Douglas bag. Oxygen consumption will be measured at baseline and then after giving albuterol and levalbuterol at times 0, 5 min, 10, 20, 40 and 60 minutes. The two medications will be given at least 4 hours apart.

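### For children prescribed a bronchodilator more often than every 4 hours, the plan's two timing rules for the second study drug cannot both be met

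*Combined protocol and SAP*

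**What the plan says.** Section F, protocol for intubated and non-intubated patients, fixes the time of the second drug in two ways.

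- **By the child's schedule.** For Group A: "On Day 1 Group A will receive albuterol first followed by levalbuterol for when the next dose is due". For Group B: "Group B will be first given levalbuterol followed by albuterol for the next scheduled dose".
- **By a minimum gap.** "The two medications will be given at least 4 hours apart".

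On day 2 the order is reversed. Oxygen consumption is measured at baseline and then "after giving albuterol and levalbuterol at times 0, 5 min, 10, 20, 40 and 60 minutes".

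The inclusion criteria in section F ask, beyond age and unit, only for a patient "with asthma, reactive airways or chronic lung disease and is scheduled to receive albuterol or levalbuterol". The two patient exclusions concern endotracheal tube leak and oxygen saturation on a raised FiO₂; neither concerns how often the child is dosed. No section gives a prescribed interval or says which timing rule prevails.

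Healthy volunteers follow a separate protocol, with one drug per day on two consecutive days. Section G plans a paired t-test of the two drugs.

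**The concern.** The two rules agree only if the child's next dose falls 4 hours or more after the first study drug. Nothing in the eligibility criteria ensures this. For a child on a shorter interval, staff must do one of three things:

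1. give the second drug at the next due dose and break the 4-hour rule;
2. hold the prescribed dose until 4 hours have passed, and so depart from the clinical order;
3. give the prescribed doses as ordered and the second study drug later, so that it is no longer the next dose.

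Each has a cost. The first shortens the only same-day separation between the drugs that the plan states. The second changes prescribed treatment for the study, which the plan does not mention. The third places beta-agonist inside the separation, where it could shift the baseline of the second session or carry over into the paired difference. Without a stated priority, different staff or shifts could choose differently, and the plan does not call for a record of what was done.

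**Working it through.** **The plan's own figure.** Section G gives 44 patients for a paired difference of 10%, SD 20%, power 0.9 and alpha 0.05. The standardised difference is 10/20 = 0.5. For a two-sided paired t-test, the noncentral t distribution gives n = 43.995, so 44. The figure reproduces, and this point does not alter it.

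**The timing rules.** Let h be the prescribed interval in hours, and let the first study drug be given at time 0.

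- Schedule rule: the second drug is given at time h.
- Gap rule: the second drug is given at time 4 or later.
- Both hold only if h ≥ 4. Otherwise the next due dose falls 4 − h hours too soon.
- If the prescribed schedule is kept and the second study drug waits for the first due time that satisfies the gap rule, that is due dose number k, where k is 4/h rounded up. It is given at k × h hours, and k − 1 prescribed doses lie between the two study drugs.

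The documents give no value of h, so the values below are assumptions that show the range.

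| h (hours) | Next due dose too soon by (hours) | k | Second drug at (hours) | Doses in between |
|---|---|---|---|---|
| 1 | 3 | 4 | 4 | 3 |
| 2 | 2 | 2 | 4 | 1 |
| 3 | 1 | 2 | 6 | 1 |
| 4 | 0 | 1 | 4 | 0 |
| 6 | 0 | 1 | 6 | 0 |
| 8 | 0 | 1 | 8 | 0 |

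If the dose is postponed instead, the second column is the length of the delay.

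**Reach.** At 4 hours or longer there is no conflict. The volunteer protocol has one drug per day and is outside the point. The measurement series lasts 60 minutes, so at an assumed 2- or 3-hour interval it ends before the next dose is due. At an assumed 1-hour interval the next dose is due at about the time of the last reading.

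**The case against.** The best defence is that the sentences can be read together: the second drug is the next scheduled dose, and a pair of sessions is run only when that dose is at least 4 hours away. Section F screens patients throughout their stay, so a child could be studied once the interval has lengthened. This may be what was meant. But the 4-hour sentence is written as a dosing instruction, not as a criterion for entry or for starting a session, and staff cannot be expected to infer one from it.

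It is also fair to say that much of the possible harm is softened or unknown:

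- A baseline is measured and section F refers to change from baseline, which would absorb some effect of an earlier dose; how much is unknown.
- The day 2 reversal means that each drug is given first on one of the days, so the data contain a comparison of first sessions that does not depend on the within-day gap. The plan does not say how the two days are combined, so neither the protection nor the damage can be fixed.
- The documents do not say which drug an intervening dose would be.

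Several stronger readings are tempting, and the documents do not support them.

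- **A stated loss of power.** This would need the share of children dosed more often than every 4 hours and the extent to which an intervening dose masks the drug difference. Neither is given. It would also depend on whether 44 or the targeted 50 per cohort complete, and on how the days are combined.
- **A plan that delays treatment.** Nothing instructs staff to hold a prescribed dose. Postponement is one possible response to the conflict.
- **Continuous dosing.** The plan speaks of due and scheduled doses in milligram amounts, which describes intermittent treatment.
- **Variation between sites.** The trial has a single center; only variation between staff and shifts is in question.

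**Conclusion.** The point holds as a contradiction between stated rules, limited to the two patient cohorts and to children prescribed a dose more often than every 4 hours. For them the schedule rule and the gap rule cannot both be followed, and the eligibility criteria do not keep such children out. If the prescribed schedule is kept, one dose intervenes at an assumed 2- or 3-hour interval and three at 1 hour.

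The textual conflict is certain. Its frequency is not, because no dosing intervals are given. The effect on the paired difference is possible but cannot be sized, and no power figure should be attached to it. The conflict is still worth resolving: it bears on prescribed treatment and on the only stated same-day separation in a paired comparison.

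**What to change.** - **Reconcile the text.** The sponsor should reconcile the timing sentences in the patient protocol with each other and with the inclusion criteria, so that every enrolled child can follow the stated timing without a prescribed dose being moved for the study. Which rule prevails is for the sponsor and the treating team.
- **Record.** Add a case report form field for any beta-agonist dose given between the two study drugs, with drug and time.
- **Analyse.** Keep all randomised pairs in the primary analysis, and prespecify a sensitivity analysis without pairs that had an intervening dose. Such pairs should not be dropped from the primary contrast. That would be an exclusion after randomisation, and possibly an informative one, since an unscheduled dose may reflect the response to the first drug; it would also cost power.

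The cost is one form field and one extra analysis. Depending on how the text is reconciled, some children may become eligible later in their stay, or not at all.

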Albuterol a β 2-adrenoreceptor agonist was first marketed in 1968 known for its bronchodilatory action. Albuterol contains a racemic mixture of two enantiomers namely the R(active form) and the L(considered inert) form. Some of the side effects of the racemic albuterol include jitteriness, anxiety and palpitations. Levalbuterol contains the single enantiomer (R – form) and is preferred in instances where the tachycardia caused by the racemate may be detrimental to the overall clinical status of the patient. However there are no studies to date that have elucidated the potential cause of the tachycardia in patients receiving albuterol attributed mainly to its β 2 receptor agonist function.

Field et al¹ measured the cost of breathing in 13 patients on mechanical ventilation as the difference between the oxygen consumption during spontaneous respiration and that during mechanical ventilation and found that the oxygen cost of breathing increases from less than 5 % of total VO₂ (oxygen consumption) in a normal resting spontaneously breathing patient to a range of 8 -24 % of total VO₂ on mechanical ventilation. Patients with cardiorespiratory or lung diseases have been shown to have elevated oxygen consumption while mechanically ventilated. β agonists can increase the oxygen consumption either by increasing minute ventilation through stimulation of the respiratory center or by directly stimulating the respiratory muscles. Furthermore there are no studies that have measured the change in oxygen consumption following administration of levalbuterol. Oxygen consumption increases in diseases states such as fever, sepsis and trauma and leads to an increased metabolic demand. Increase in oxygen consumption that is disparate to the oxygen delivery leads to anaerobic metabolism and lactic acidosis and can further worsen the clinical status or delay recovery. Also there may be impaired oxygen extraction or use at the cellular level i.e. cytopathic hypoxia thus creating a functional arteriovenous shunt. Maintaining adequate oxygen delivery to meet the metabolic demands is fundamental in treating critically ill patients.

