In a follow up study by [name] et al⁴ in 1997 studied the effects of Bronchodilators on Spontaneous Ventilation and Oxygen Consumption in anesthetized intubated Rhesus Monkeys showed that racemic albuterol caused an increase in Oxygen consumption of 45% and minute ventilation of 50%. These changes were suppressed in the presence of a β blocker such as propranolol. Therefore the increase in oxygen consumption could be secondary to β adrenoreceptor stimulation resulting in stimulation of the respiratory center or due to increased metabolic demands.

β agonists are used extensively in pediatric patients with chronic lung disease, asthma or for its mucolytic property. Many of these children are admitted primarily for another condition for example septic shock, in which case their oxygen demands may already be increased. In such conditions administering β agonists that may further increase oxygen consumption and oxygen costs of the body may have deleterious effects on the overall clinical status of the patient.

C. Hypothesis: Levalbuterol does not increase oxygen consumption to an extent that is increased by salbutamol (albuterol).

D. Purpose of this Study: The purpose of our study is to study the peak oxygen consumption in subjects scheduled to receive albuterol and compare it with that of levalbuterol using a non-invasive method with the Innovision Innocor machine. To date, no known human studies that have measured the change in oxygen consumption after levalbuterol.

1. Study Objectives

Primary objective is to measure the peak oxygen consumption at baseline and then after the administration of albuterol and levalbuterol inhalation in patients admitted to or currently cared for in the pediatric intensive care unit (PICU) or cardiothoracic intensive care unit (CTICU) at Children's Hospital Los Angeles with asthma reactive airway or chronic lung disease.

Secondary objectives are to collect change in Cardiac output, systemic vascular resistance, stroke volume, minute ventilation, heart rate, blood pressure, respiratory rate, pulse oximetry with each intervention.

E. Significance and preliminary studies

Albuterol has been in used in the treatment of asthma to relieve bronchospasm for nearly 45 years. However numerous reports have associated long term use of racemic albuterol with increasing morbidity and mortality. Mechanisms underlying these observations are not well known at this point.

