Recent studies have shown that the S enantiomer has bronchoconstricting and pro-inflammatory properties which may be counterbalanced by the R enantiomer in the racemate. Numerous studies have been reported to question the clinical efficacy of racemic albuterol or in fact that the racemate may actually have deleterious effects on the bronchioles. Racemic albuterol consists of 50% each of the active and the inactive isoform. However there is accumulating body of data from animal studies questioning the inactive or rather the counteractive nature of the S isoform.

Although β 2 agonists have been in use for a long time, controversies exist as to their efficacy and safety over long term use. Animal studies focusing on the long term use of racemic albuterol have shown that it increased airway hyper responsiveness, edema and susceptibility to spasmogens. These effects have been understood to be from the S isoform as previous clinical trials have demonstrated the individual bronchodilator properties of the R isoform along with suppression of pro inflammatory mediators.

Mazzoni et al⁵ have reported that bronchospasm in sensitized animals was completely suppressed by an infusion of racemic albuterol, however a more prolonged infusion longer than 1 hour increased their susceptibility to the antigen and induced hyper responsiveness to histamine. This progressive loss of efficacy of racemic albuterol with time is speculated to be from disproportionate accumulation of the S enantiomer due to stereospecific metabolism of the R enantiomer.

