The Innocor device has the ability to measure cardiac output by mixing in small amounts of Nitrous Oxide (N₂O) and Sulfur Hexafluoride 6 (SF₆). Oxygen consumption is measured by the Innocor device without the addition of these gases. For this study N₂O and SF₆ will not be used. No part of the Innocor device will be attached to the skin for the purposes of this research. The Innocor device can be used to measure pulmonary function tests requiring some degree of cooperation from subjects. It is possible to obtain measurements of oxygen consumption using the Innocor device in intubated, sedated patients without their cooperation. For non-intubated patients, they would only need to be able to follow the direction to breathe out through the sensor. No timing of breaths are required.

Protocol for Healthy Adult Volunteers

After obtaining a written informed consent from the volunteer, the subject will be randomized using pre-prepared opaque sealed envelopes to which medication (albuterol or levalbuterol) they receive first. The measurements will be obtained over 2 consecutive days. The dosage of

Albuterol will be 5 mg mixed with 2 to 3 ml of saline and will be aerosolized over 10 minutes. The dosage of levalbuterol will be 1.25 mg mixed with 2 to 3 ml of saline and will be aerosolized over 10 minutes. On day 1 of the study the patient will receive the medication they were randomized to. At approximately the same time of day on day 2 the subject will receive the other medication. Following each breathing treatment, oxygen consumption will be measured using the non-invasive Innocor machine. Oxygen consumption will be measured at baseline and then following the medication at times 0, 5 min, 10, 20, 40 and 60 minutes. Temperature will be measured prior to the aerosolized medication and heart rate, blood pressure, oxygen saturations, and respiratory rate will be measured at intervals over the 60 minutes of oxygen consumption measurement.

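### In the healthy-volunteer cohort, drug and R-albuterol dose change together (2.5 mg R against 1.25 mg R), so an albuterol-higher or null result there cannot be separated from R dose.

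*Combined protocol and SAP*

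**What the plan says.** The volunteer doses are fixed in the Protocol for Healthy Adult Volunteers: "Albuterol will be 5 mg mixed with 2 to 3 ml of saline" in one session and "The dosage of levalbuterol will be 1.25 mg mixed with 2 to 3 ml of saline" in the other. No reason is given for the pairing.

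The opening background says "Albuterol contains a racemic mixture of two enantiomers namely the R(active form" and an inert form, and that levalbuterol is the R form alone. Section E adds: "Racemic albuterol consists of 50% each of the active and the inactive isoform".

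For ICU patients, the protocol section for intubated and non-intubated patients ties the two doses together. When albuterol is the prescribed drug, "the levalbuterol dose will be chosen to be ½ that milligram amount"; when levalbuterol is prescribed, albuterol is set at twice its milligrams. The same section then lists typical ICU doses, with albuterol at a "minimum of 2.5 mg and maximum of 5 mg and levalbuterol 0.63 mg and 1.25 mg respectively", and in a parenthesis treats 1.25 mg as a ceiling ("1.25 mg(max dose of levalbuterol").

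The hypothesis in section C is "Levalbuterol does not increase oxygen consumption to an extent that is increased by salbutamol (albuterol"). Section G expects the reverse, a smaller rise with the racemate. It specifies a paired t-test in children and sets a target of 50 subjects in each of the three cohorts. It gives the volunteers no separate question, analysis or interpretation.

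**The concern.** A crossover removes differences between people. It does not remove a difference that travels with the treatment in every person. Here R dose is twice as high in each volunteer's albuterol session, so drug and R dose are completely confounded in that cohort.

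The imbalance favours the section C hypothesis: more R with albuterol could give a larger VO2 rise even if the enantiomers make no difference. It works against the section G expectation, because a truly larger levalbuterol effect per milligram of R could be cancelled by the smaller dose. Dependence on R dose is plausible on the protocol's own account, since the background reports that propranolol suppressed the rise in monkeys and suggests β-receptor stimulation as a cause.

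The patient rule matches R, so the volunteer cohort addresses a different question under the same hypothesis. The interpretation of one cohort of 50 is at stake.

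**Working it through.** **1. The plan's own figure.** Paired t-test, two-sided α = 0.05, difference 10%, SD 20%, power from the noncentral t with noncentrality (d/SD)√n. n = 43 gives 0.893 and n = 44 gives 0.900, so the stated 44 reproduces. n = 50 gives 0.934. Section G does not state sidedness; two-sided reproduces its figure.

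**2. R dose.** R = 0.5 × mg racemate, or 1.0 × mg levalbuterol.

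- Volunteers, albuterol session: 0.5 × 5 = 2.5 mg R.
- Volunteers, levalbuterol session: 1.25 mg R.
- Ratio: 2.5/1.25 = 2.0.

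**3. Milligram ratios (2:1 matches R).**

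| Where | Albuterol / levalbuterol | Ratio |
|---|---|---|
| Volunteers | 5 / 1.25 | 4.0 |
| Patient half rule | by definition | 2.0 |
| Young-child example | 1.25 / 0.63 | 1.98 |
| Typical ICU, lower pair | 2.5 / 0.63 | 3.97 |
| Typical ICU, upper pair | 5 / 1.25 | 4.0 |

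The half rule takes levalbuterol above 1.25 mg once albuterol exceeds 2.5 mg, which at 0.15 mg/kg is above 2.5/0.15 = 16.7 kg.

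**4. How large could a pure dose effect be?** This step rests on assumptions. Suppose the drugs are identical per milligram of R, albuterol 5 mg raises VO2 by E, and halving R removes a fraction f of that rise (0 = flat, 0.5 = proportional). The apparent difference is E × f. E = 5.2% is the monkey pilot in section G, (5.26 − 5.0)/5.0, where the drug is not named. E = 10% and 20% are illustrative. Chance of a significant difference with n = 50:

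| E | f = 0 | f = 0.25, SD 20% | f = 0.5, SD 20% | f = 0.25, SD 30% | f = 0.5, SD 30% |
|---|---|---|---|---|---|
| 5.2% | 5% | 7% | 15% | 6% | 9% |
| 10% | 5% | 14% | 41% | 9% | 21% |
| 20% | 5% | 41% | 93% | 21% | 64% |

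At E = 20% and f = 0.5 the artefact is 20 × 0.5 = 10 points, the whole difference the study is sized to detect.

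**5. Masking.** Suppose that at 2.5 mg R levalbuterol raises VO2 by 10 points more than albuterol, whose own rise is A. The observed difference is (A + 10)(1 − f) − A. Chance of a significant levalbuterol-higher result with n = 50:

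| A | f | Observed difference | SD 20% | SD 30% |
|---|---|---|---|---|
| any | 0 | 10 | 93% | 64% |
| 5.2% | 0.25 | 6.2 | 57% | 30% |
| 5.2% | 0.5 | 2.4 | 13% | 8% |
| 10% | 0.25 | 5.0 | 41% | 21% |
| 10% | 0.5 | 0 | 2.5% | 2.5% |

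**The case against.** The volunteer doses have a visible source: they are the upper pair of typical ICU doses in the patient section. At 0.15 mg/kg the 5 mg cap is reached at 5/0.15 = 33.3 kg, so essentially every adult would be on 5 mg. Section C names two drugs and does not say per milligram of R. Comparing two usual regimens is legitimate, and the result would be a valid randomised comparison of the doses given. All of this stands. What is missing is any statement that this is the volunteer question.

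A reader might infer that an albuterol-higher or null result cannot be due to the drug at all. The documents do not support that: they give no dose-response, and a flat one would produce no artefact. The defensible statement is that drug and R dose cannot be separated.

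A reader might also infer that the trial's main comparison is compromised. It is not where the half rule is followed, because the primary objective concerns ICU patients and that rule matches R. The patient section does leave a doubt, since the 4:1 typical doses and the 1.25 mg ceiling sit beside the half rule. Read literally, the half rule applies. If staff cap levalbuterol at 1.25 mg instead, heavier children would be unmatched too. That is a separate clarification.

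The probabilities are illustrative. The fraction f and the 10% and 20% rises are assumed, SD 20% is the planning value for children, and section G itself doubts that variability is the same across cohorts. The masking case also leans on section G's expectation, which runs opposite to section C. Section G credits the 46% rise to L-Albuterol where the background credits such rises to the racemate, so drug names may have been exchanged there.

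**Conclusion.** The point holds for the healthy volunteers, one of three cohorts with 50 planned. The twofold R difference follows directly from the protocol's own figures. Its effect on VO2 is unknown: none if the response is flat. Under the assumptions shown with SD 20%, the chance of a significant result from dose alone is 7% to 15% for a 5.2% rise and up to 93% for a 20% rise. Power to show a true 10-point levalbuterol excess could fall from 93% to between 57% and 2.5%.

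One outcome survives: a levalbuterol-higher result would be evidence of a drug difference, provided more R does not lower VO2. The sample-size calculation is not in error. This should be fixed because it changes what the volunteer cohort can support and the remedy is cheap.

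**What to change.** **Main change, in the Protocol for Healthy Adult Volunteers and section G.** State that:

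- the volunteer comparison is between two dose regimens, albuterol 5 mg and levalbuterol 1.25 mg, and why those doses were chosen;
- an albuterol-higher or null volunteer result will not be read as evidence about the enantiomers or as confirmation of the patient result;
- a levalbuterol-higher result may be read as a drug difference if more R does not lower VO2;
- volunteers will not be pooled with R-matched patients.

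This is a wording change with no loss of power. Its price is a narrower volunteer conclusion.

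**Alternative, for the clinical team.** Match volunteers at 2:1, for example albuterol 2.5 mg with levalbuterol 1.25 mg. This changes the intervention and needs an amendment. It may also shrink what can be measured. If a 10-point drug difference at 2.5 mg R scales with f = 0.25 or 0.5, it becomes 7.5 or 5 points. Power with 50 volunteers (SD 20%) then falls from 93% to 74% or 41%, and 90% power would need 77 or 171 volunteers. Matching at 5 mg with 2.5 mg would exceed the levalbuterol maximum the protocol names.

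**Secondary clarification, in the patient section.** Say whether the half rule or the 1.25 mg figure governs when albuterol exceeds 2.5 mg, and record the doses actually given. The cost is a sentence and a data field.
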